#### **6.4.4. Concomitant Medications and Nondrug Treatments**

Prior treatment are the ones stopped prior to Day 1 of study treatment. Concomitant treatments are the ones taken on Day 1 or after. Prior drug and non-drug treatment, concomitant drug (including SoC) and non-drug treatment will be summarized by treatment group. Number and percent of subjects used additional immunomodulatory agent (i.e., IL-6 targeting therapy), or other non-FDA approved, compassionate use or expanded access treatment will be reported by treatment group.

#### **6.5. Safety Summaries and Analyses**

The safety endpoints are listed in Section 3.5. All safety analyses will be performed on the SAS (Section 4).

For the categorical (including binary) endpoints, results will be analyzed as described in Section 5.2.1 by treatment group.

For continuous endpoints, results will be analyzed as described in Section 5.2.2 by treatment group.

#### **7. INTERIM ANALYSIS**

No interim analysis will be performed. Safety data will be reviewed by a Yale DSMB.

The first safety review was conducted after randomization of 24 subjects and there was no further review as additional patients were not enrolled.

## APPENDICES

### Appendix 1. Definition and Use of Visit Windows in Reporting

The data will be analyzed at each scheduled visit per defined in section 6.3.1 of the study protocol.

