6.3 Study Procedures

6.3.1 Study Schedule

Visit Identifier ^{Error!} Reference source not found.	Screening	Day 1	Daily assessments (days 2-14) ^{c,d}	Early Termination/ Discontinuation/ End of Treatment (Day 14 or Discharge)	Follow-up ^{Erro} r! Reference source not found. (Dav 28)	Follow-up (Day 60)	Follow up (Day 90)	Early Termination/ Discontinuation
Visit Window	48 hours prior				+/-3 days			
	to Day 1							
Informed consent	х							-
Medical history	х							
Physical examination ^d	х	х	х	Х	Х			
Weight ^d	Х							
Vital signs ^d (pulse, blood pressure, respiratory rate ^e , temperature ^f)	Х	×		X	Х			
Laboratorv ^d			х					
Hematology	X		X		N N			
	X	X	Χ	X	X			
Blood chemistry	х	х	Х	Х	х			
Coagulation ^g	Х	х	х	Х	х			
Inflammation panel ^h	х	х	х	Х	Х			
Cardiac panel ⁱ	х	х	х	Х	х			
Pregnancy test	Х				Х			
Oxygen saturation by pulse oximetry (SaO ₂) ^d	Х	х	х	Х	Х			
12 Lead ECG ^d	Х	х	х	Х	Х			
Record if admitted to intensive care unit (ICU)	Х	х	х	Х	х			х
Registration/randomization		х						
Study drug administration		х	х	Х				
NIAIA Ordinal scale of disease severity	х	х	х	Х	х	х	х	х

APPROVED BY THE YALE UNIVERSITY IRB 9/28/2020

Protocol 2000027848

Version R5; 15 SEPTEMBER 2020

Visit IdentifierError! Reference source not found.	Screening	Day 1	Daily assessments (days 2-14) ^{c,d}	Early Termination/ Discontinuation/ End of Treatment (Day 14 or Discharge)	Follow-up ^{Erro} r! Reference source not found. (Day 28)	Follow-up (Day 60)	Follow up (Day 90)	Early Termination/ Discontinuation
Visit Window	48 hours prior				+/-3 days			
	to Day 1							
Record hospitalization status	х	х	х	Х	х	х	х	х
Assessment signs and symptoms of pneumonia		х		Х	х	х	х	
FiO2	х	х	х	х				
supplemental oxygen	х	х	х	х				
Blood for exploratory analysis ⁱ		х	Day 7	х	х			
Paxgene sample for exploratory biomarker analysis ^k		х	Day 7	х				
Plasma, Saliva and/or nasal swab for SARS-CoV-2 and exploratory analysis ^m		х	Day 7	х				
Whole blood for FACS analysis ⁿ		х	Day 7	х	x			
Concomitant treatment(s)		Х	Х	Х	X			Х
Adverse event monitoring	Х	Х	Х	Х	×	Х	Х	X□

Visit Identifier ^{Error! Reference source} not found.	Screening	Day 1	Daily assessments (days 2-14) ^{c,d}	Early Termination/ Discontinuation/ End of Treatment (Day 14	Follow-up ^{Erro} r! Reference source not found.	Follow-up (Day 60)	Follow up (Day 90)	Early Termination/ Discontinuation
Visit Window	48 hours prior to Day 1			or Discharge)	(Day 28) +/-3 days			

a. Day relative to start of study intervention (Day 1).

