- b. Contact may occur via telephone contact and will occur up to 90 days from administration of the final dose of study intervention. Procedures listed for Follow-up Visit 1 (with exception of ordinal scale of disease severity, hospitalization status, supplemental oxygen/ventilatory support status, contraception check, concomitant medications, and AE/SAE monitoring) will only be performed if the participant is hospitalized. Otherwise these visits will be remote phone or telemedicine visits.
- c. Assessments will be performed at least daily while hospitalized by the clinical service. Vital signs may be more frequent (eg, every 4 8 hours), per hospital practice.
- d. Collected as per hospital standard of care practice
- e. Note if spontaneous or mechanical ventilator setting
- f. Note if oral, rectal, or core

L

- g. Will include PT/PTT, fibrinogen, D-Dimers
- h. Inflammation will include as available: hsCRP, ferritin, procalcitonin, fibrinogen, LDH, etc.
- i. Cardiac panel will include as available: high sensitivity troponin, BNP, etc.
- j. Cytokine panel will include, as available: IL-1, IL-2, IL-6, IL-8, IL-17A, IL-17F, TNF-α, IP-10, IFNγ, CCL5, etc. Sample will be used for cytokine assessment that may include but is not limited to IFNγ, IL-1β, IL-4, IL-6, IL-10, IL-12p70, TNFa, IP-10, and IL-2R. This sample may also be banked and/or used for additional post-hoc analyses related to COVID-19 and/or the mechanism of action of treatments administered in this study, including IgG and IgM antibodies to COVID-19.
- k. Paxgene sample (optimized for RNA analysis) may be banked and/or used for exploratory assessments related to COVID-19 and/or the mechanism of action of treatments administered in this study.
 - Physical examination by a clinician will be individualized according to participant status
- m. Plasma, saliva and/or nasal swab will be collected and tested for SAR-CoV2 should by performed by polymerase chain reaction (PCR), or other commercial or public health assay in any specimen prior to randomization and on an ongoing basis, as needed for patient care and per policy at YNHH. Samples may also be used for additional analyses related to COVID-19 and/or the mechanism of action of treatments administered in this study.
- n. Whole blood sample may be collected as available for analysis of lymphocyte subsets by flow cytometry.

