6.3.4 Enrollment

After Screening, if the subject meets criteria, they will be enrolled. Baseline labs including hsCRP, ferritin, LDH, D-dimer, CBC, and CMP will be measured twice daily (per SOC). Research blood samples will be obtained prior to drug administration on Day 1 and then again on Day 2 and every 48 hours thereafter. All subjects will be randomized to either tofacitinib 10 mg twice daily or SOC. Patients will be monitored at least once daily after initiation of therapy during the duration of their hospitalization, and will be followed up after discharge.

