6.3.6 End of Study and Follow-up

After patients complete study treatment, they will be contacted to follow up on their condition. This may occur via telephone or telehealth and will occur on day 28 +/- 3 days after the time of enrollment and then again at days 60 and 90 days. On day 28 follow-up, blood sample for exploratory analysis may be collected. At the time of follow up visits/calls, patients will be asked about:

- Adverse events
- Concomitant therapies
- All efforts will be made to contact subjects for follow-up, including: telephone calls, texts, and emails to the subject and/or close contacts. Vital status of all subjects will be ascertained either by contacting the subjects and/or subjects' close contacts or by a vital records search.

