### 2.2. Study Objectives, Endpoints, and Estimands

Objectives/ Endpoints	Type of Endpoints [categorical (including binary), continuous, or time to endpoints]
Primary	
The primary objective of this study is to determine whether tofacitinib improves the clinical outcomes of patients with moderate SARS-CoV-2 infection as determined by the Primary outcome measure.	Binary endpoint

Endpoint: Proportion of subjects alive and not needing any form of mechanical ventilation, high flow oxygen, or ECMO by day 14 and day 30.	
Secondary	
Clinical improvement (defined as a 2-point increase) as measured by NIAID 8-point ordinal scale (i.e., 1 = death and 8 = Not hospitalized, no limitations on activities) at day 14.	Categorical endpoint
Clinical status using ordinal scale (days 3 through day 14): The ordinal scale is an assessment of the clinical status at the first assessment of a given study day. The scale is as follows: 1) Death; 2) Hospitalized, on invasive mechanical ventilation or extracorporeal membrane oxygenation (ECMO); 3) Hospitalized, on non-invasive ventilation or high flow oxygen devices; 4) Hospitalized, requiring supplemental oxygen; 5) Hospitalized, not requiring supplemental oxygen - requiring ongoing medical care (COVID-19 related or otherwise); 6) Hospitalized, not requiring supplemental oxygen - no longer requires ongoing medical care; 7) Not hospitalized, limitation on activities and/or requiring home oxygen; 8) Not hospitalized, no limitations on activities.	Categorical endpoint
Time to recovery (Day of recovery is defined as the first day on which the subject satisfies one of the following three categories from the clinical status of ordinal scale: 6) Hospitalized, not requiring supplemental oxygen - no longer requires ongoing medical care; 7) Not hospitalized, limitation on activities and/or requiring home oxygen; 8) Not hospitalized, no limitations on activities) through day 14 and day 30 from day 1.	Time to endpoint.
Time to clinical improvement (defined as a 2-point increase on the ordinal scale).	Time to endpoint
Clinical status on ordinal scale at day 30, 60, and 90.	Categorical endpoint
Mortality rate at day 30, 60 and 90.	Binary endpoint
Proportion of patients requiring ICU admission and mechanical ventilatory support (defined as clinical status of 2 and hospitalization status = ICU) at 14 and 30 days.	Binary endpoint

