### **5.2.3. Analyses for Time-to-Event Endpoints**

For time to recovery and time to clinical improvement

- If subject died prior to or on the specified time point (Day 14 or Day 30), the result for time to event will be censored on the date of death regardless of if subjects have experienced recovery or clinical improvement prior to Death.
- If no death is recorded through the specified time point (Day 14 or Day 30): For a participant who experiences the event of recovery/clinical improvement through Day 14 or Day 30, the time to event will be the study day corresponding to the earliest visit date at which the participant has already experienced the event.
- For all participants who have not experienced the event, their time to event will be right censored at the last available measurement time of the clinical status through Day 14 or Day 30.

Time to event endpoints will be analyzed using the Estimand with treatment policy strategy specified in Section 2.2.1.

The number of participants, number and percent of participants censored, and participants with recovery or clinical response will be provided for each treatment group. The median and quartiles time to event will be estimated by the Kaplan-Meier method.

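### The SAP reports outcomes at or through Day 30, but the schedule has no Day-30 visit, no rule maps the Day 28 ± 3 contact to Day 30, and late events are dated by visit rather than by the day they happen

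*SAP*

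**What the plan says.** **Endpoints at Day 30.** SAP 2.2 gives the primary endpoint as "Endpoint: Proportion of subjects alive and not needing any form of mechanical ventilation, high flow oxygen, or ECMO by day 14 and day 30". It also lists "Mortality rate at day 30, 60 and 90", ordinal status at Day 30, time to recovery followed through Day 30, and ICU admission with ventilation at 30 days. SAP 5.2.3 applies a Day-14 or Day-30 limit to time to recovery and time to clinical improvement.

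**Visits.** In the schedule in Protocol 6.3.1, the column for inpatient assessment is headed "Daily assessments (days 2-14". After it come an end-of-treatment column (Day 14 or discharge) and follow-up at Days 28, 60 and 90. Protocol 6.3.6 says that contact "will occur on day 28 +/- 3 days after the time of enrollment and then again at days 60 and 90 days".

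**Link between the two.** SAP Appendix 1 carries a title that promises visit windows, but its only content is "The data will be analyzed at each scheduled visit per defined in section 6.3.1 of the study protocol". SAP 5.3 allows no imputation.

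**Dating of events.** SAP 2.2 and 3.2 define recovery by the first day on which category 6, 7 or 8 is met. SAP 5.2.3 says "the time to event will be the study day corresponding to the earliest visit date at which the participant has already experienced the event". Patients without an event are censored at their last status measurement within the limit.

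**The concern.** Two programmers following this SAP could produce different Day-30 tables. One would carry a Day-25 contact forward as Day-30 status, and the other would report Day 30 as missing. One would count an event found at a Day-31 contact, and the other would censor it.

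The dating rule adds a second problem. A visit at which the event has already happened can fall later than the event. Up to Day 14 daily inpatient assessment largely hides this. After Day 14 the schedule has no daily column, so a literal reading gives a recovery curve that is flat from Day 14 to about Day 25 and then jumps. With hypothesis testing dropped, the proportions and Kaplan-Meier medians are the whole efficacy result, so their definition matters.

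**Working it through.** The plan gives no figure on this point. Its power statement concerns the Day-14 comparison and does not enter here.

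**1. The contact window.** From Protocol 6.3.1 and 6.3.6: 28 − 3 = 25 and 28 + 3 = 31, which is seven permitted days.
- Days 25–29 (5 of 7) precede Day 30. A contact on Day c leaves 30 − c days unobserved: 5 days at c = 25, 1 day at c = 29.
- Day 30 itself is 1 of 7.
- Day 31 (1 of 7) is in window but beyond the time-to-event limit.

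The footnotes to the schedule count Day 1 from the start of study drug, while Protocol 6.3.6 counts from enrolment. If 28 days means elapsed days from an enrolment on Day 1, the window is study Days 26–32 and 2 of 7 days lie beyond Day 30. If contacts are spread evenly over the window (an assumption), 1/7 = 14% to 2/7 = 29% fall outside the limit.

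**2. Delay if only scheduled visits count.** Delay = contact day − event day, for events on Days 15–24.
- Contact on Day 28: from 28 − 24 = 4 to 28 − 15 = 13 days late.
- Contact on any of Days 25–30: from 25 − 24 = 1 to 30 − 15 = 15 days late.
- Contact on Day 31: no event within the limit, so censored at the last earlier scheduled measurement, Day 14.

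**3. Are the true dates available?** A discharged patient is in category 7 or 8, and so has recovered. A living patient of known status who has not recovered by Day 14 is therefore in category 2–5 and in hospital. For improvement, moving from category 5 or below to category 7 is a gain of at least 7 − 5 = 2 points, so a patient who entered in those categories and has not improved by Day 14 is also in hospital. For inpatients, a schedule footnote says "Assessments will be performed at least daily while hospitalized by the clinical service", and Protocol 6.3.4 says "Patients will be monitored at least once daily after initiation of therapy during the duration of their hospitalization". Protocol 6.2.1 adds daily review of the medical record. The day of recovery, improvement or discharge can therefore be found.

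**4. Illustration of the scheduled-visits-only reading.** The data are invented: an arm of 12, five patients recover on Days 5, 7, 9, 11 and 13, four go home on Days 15, 16, 18 and 20, and three do not recover.
- True dates: 6/12 have recovered at Day 15, so the median is Day 15. By Day 24, 9/12 = 75% have recovered.
- Last four dated at a Day-28 contact: 5/12 = 42% have recovered by Day 24, and the median is Day 28.
- All seven late patients contacted on Day 31 and censored at Day 14: the curve stops at 42% and the median is not reached.

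Had six or more of the 12 recovered by Day 14, the median would be the same under either rule.

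**The case against.** The strongest reply is step 3: the patients whose dates are in doubt are in hospital and seen daily, so no recovery need be dated at the follow-up contact. Appendix 1 says data are analysed at each scheduled visit, and does not say only there. The end-of-treatment column may also be read as covering discharges after Day 14. This stands as far as it shows that the dates exist. It does not settle whether they will be used. The footnote is attached to the Days 2–14 column, Protocol 6.3.5 heads its daily assessments as Days 1–14, and the SAP never says that later inpatient records feed these endpoints. Status is also taken at the first assessment of the day, so a patient discharged that afternoon may have no later category recorded in hospital.

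A reader might infer more than the documents support:
- **That no patient is assessed on Day 30.** Day 30 lies inside the window, and inpatients are seen daily.
- **That Day-30 mortality cannot be determined.** Protocol 6.3.6 provides for later contacts and a vital-records search. The SAP only omits to say that the date of death is used.
- **That a Day-31 contact is lost for every endpoint.** The through-Day-30 limit governs the time-to-event endpoints only. Assigned by nominal visit, that contact would count for status, support and ICU.
- **That the primary result is at risk.** SAP 3.1 and 6.1 keep the primary endpoint at Day 14, and SAP 3.2 does the same for time to recovery.
- **That the illustration forecasts the result.** It places the arm one recovery short of its median at Day 14. The case with no median needs all four late recoverers contacted on Day 31, which has probability (1/7)^4 = 1/2401 if contacts are independent and evenly spread. An arm of 12 also assumes 24 patients (SAP section 7) split 1:1 as in the protocol, whereas SAP 2.3 says 2:1.

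The mismatch is also not the SAP's alone, because the protocol itself lists ordinal status and mortality at Day 30.

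**Conclusion.** The point holds in a limited form. The Day-30 outcomes have no matching visit and no mapping rule: 5 of the 7 permitted contact days precede Day 30, and 1 of 7 (2 of 7 if days are counted as elapsed from enrolment) lies beyond the time-to-event limit. The visit-date rule in SAP 5.2.3 conflicts with the definition of recovery by first day. On the scheduled-visits-only reading, events on Days 15–24 are dated 1 to 15 days late or censored at Day 14.

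The size in this trial cannot be fixed from the documents. It depends on how many patients recover or improve after Day 14 and on whether later inpatient records are used. If nobody does so after Day 14, the dating rule has no effect on those days. If inpatient records are used, most of the dating error disappears, but the missing mapping to Day 30 remains. The SAP reports no tests and about 24 randomised patients, so what changes is descriptive proportions and medians. The correction is cheap and should be made.

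**What to change.** Amend the SAP as follows, and align the protocol's Day-30 wording with it.
- **Appendix 1:** assign the Day 28 ± 3 contact (Days 25–31) to one analysis time point for ordinal status, respiratory support and ICU, and label it Day 28 or Day 28–30. State the study-day origin.
- **Mortality:** derive Day-30 mortality from the date of death, using later contacts and the vital-records search.
- **Section 5.2.3:** for both time to recovery and time to clinical improvement, date the event at the first day the criterion is met in the inpatient record, or at discharge if that comes first. This keeps recovery in hospital (category 6) and improvement in hospital. Censor at the last known status, and count in-window contacts up to Day 31.
- **Consistency:** reconcile the Day-30 wording in 2.2 and 5.2.3 with the Day-14-only wording in 3.1, 3.2 and 6.1.

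The cost is SAP wording, a changed label and modest reprogramming. The inpatient, discharge and death dates should already be in the hospital record or within reach of the planned follow-up, so no new patient contact is needed.

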### Appendix 2. List of Abbreviations

Abbreviation	Term
AE	adverse event
BID	twice daily
CCL5	C-C motif chemokine ligand 5
CI	confidence interval
COVID-19	Corona Virus Infectious Disease-19
CRF	Case Report Form
ECG	electrocardiogram
ECMO	extra-corporeal membrane oxygenation
FAS	full analysis set
FDA	Food and Drug Administration (United States)
hs-CRP	high-sensitivity-C-reactive protein
ICU	Intensive Care Unit
IL	interleukin
IP-10	interferon gamma-induced protein-10
LDH	lactate dehydrogenase
MAX	Maximum
MIN	Minimum
N/A	Not Applicable
NIAID	National Institute of Allergy and Infectious Diseases
PT/PTT	prothrombin time/partial prothrombin time
SAE	serious adverse event
SAP	statistical analysis plan
SARS-CoV-2	Severe Acute Respiratory Syndrome-Coronavirus-2
SAS	safety analysis set
SD	standard deviation
SoC	standard-of-care
TEAE	treatment-emergent adverse event
TNF	tumor necrosis factor

